Study Population: As discussed above, neonates have unique aspects of their coagulation cascade that warrant specific biological consideration. This study will be a single-center prospective, randomized control trial. After informed and written parental consent, a total of 36 neonates (age less than 30 days) undergoing elective cardiac surgery with cardiopulmonary bypass will be enrolled at Children's Healthcare of Atlanta. The following criteria will be used to determine patient eligibility:

Inclusion Criteria:

1. Full term neonates (36-42 weeks gestational age)
2. Infants \leq 30 days of age at time of surgery
3. APGAR score of 6 or greater at 5 minutes after delivery
4. Neonates undergoing elective cardiac surgery requiring CPB at Children's Healthcare of Atlanta
5. Parents willing to participate and able to understand and sign the provided informed consent

Exclusion Criteria:

1. Preterm neonates (less than 36 weeks gestation)
2. Patients undergoing an emergent procedure or surgery not requiring CPB
3. Patients with personal or family history of a coagulation defect or coagulopathy
4. Parents unwilling to participate or unable to understand and sign the provided informed consent

Recruitment and Enrollment After a patient is deemed eligible for the study, informed and written consent will be obtained from the parents or legal guardian. Only those patients who meet the entry criteria will be approached for study participation. There will be no costs for the participants. At any time, parents and legal guardians will have the option of withdrawing their child from the study.

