Randomization As they present to Children's Healthcare of Atlanta, patients will be enrolled consecutively and randomized to receive either FC or cryoprecipitate as part of a standardized transfusion algorithm. Once on CPB, patients will be randomized using block randomization with variable blocks. Patients will be randomly assigned (1:1) to receive either cryoprecipitate (control group) or fibrinogen concentrate (FC) (study group) as part of our post-bypass transfusion algorithm. Ideally, all practitioners would be blinded to the study. However, the dose of fibrinogen concentrate is diluted in normal saline and may be up to approximately 50mls. The use of a placebo would require the administration of up to 50mls of normal saline, 20% of a blood volume in a 3kg neonate. The hemodilutional effects of placebo would potentially confound the results comparing the two groups. Therefore, the anesthesiologist, who will be administering either cryoprecipitate or FC, will be aware of the group allocation. Parents, surgeons, and critical care physicians will be blinded to the group allocation.

Rationale for Standardized Anesthetic, Cardiopulmonary Bypass and Anticoagulation Management In order to minimize confounding factors, we will follow our standard anesthetic management, cardiopulmonary bypass protocol, and anticoagulation strategy.

Anesthesia Management and Cardiopulmonary Bypass Management

Anesthesia, CPB, and surgery will be performed by the same teams of anesthesiologists, perfusionists, and surgeons. Anesthesia techniques will follow institutional protocol, which include a balanced anesthesia technique and necessary invasive monitoring, including arterial and central pressure monitoring.

Cardiopulmonary Bypass management

Nonpulsatile CPB is performed using a nonheparin-coated system, a Terumo FX-05 hollow-fiber membrane oxygenator (Terumo Cardiovascular Systems, Ann Arbor, MI), and Livanova SMArt-coated neonatal circuit (LIVANOVA USA (Sorin Group USA),

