Arvada, CO, USA). All circuits contain a 250-300 ml priming volume, which include 50ml 25% albumin (Grifols), Plasmalyte, 0.5mg/kg mannitol, calcium gluconate, and 8.4% sodium bicarbonate to normalize the pH. Packed RBCs (pRBCs) are added to the circuit as needed to achieve and maintain a hematocrit of 30% throughout the duration of CPB. In accordance with institutional policy, patients having cardiac surgery receive pRBCs that are less than 14 days old. 50ml fresh frozen plasma (FFP) is added to CPB prime and another 50 ml FFP is added upon re-warming. Conventional or zero-balance ultrafiltration is performed throughout the bypass period at both institutions. For all patients, pH-stat blood gas management is used during bypass.

Anticoagulation

Anticoagulation is established with 500units/kg of porcine heparin with 1000 units of heparin added to the CPB prime. Kaolin-activated ACT values greater than 480 seconds are confirmed prior to the initiation of CPB (i-STAT®1 Analyzer; Abbot Point of Care Inc, Abbott Park, IL, USA). Additional heparin is administered as necessary during CPB to maintain an ACT >480 seconds. After completion of surgery, patients are rewarmed to 36°C and weaned from CPB. Protamine (5mg/kg) is used to neutralize heparin upon completion of CPB and confirmed with ACT. Additional protamine is administered if ACT levels are above baseline values. All neonates (patients <30 days of age) will receive anti-fibrinolytic therapy. Tranexamic acid was used: 100mg/kg bolus dose pre-bypass, 100mg/kg bypass dose, and an infusion at 10mg/kg/hr that was terminated at transport to the ICU.

Transfusion Algorithm: In order to minimize confounding factors, a transfusion algorithm and transfusion thresholds will be followed in the operating room and ICU for all patients enrolled in the study. RBCs will be transfused for hematocrit <32% for acyanotic neonates, while cyanotic neonates are transfused RBCs for a goal Hct 35-40%. RBC transfusion is not permitted for hematocrit values higher than 45%.

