Aim 2 (Correlation of clot properties to clinical outcomes): Clinical outcome variables will be collected for each patient and correlated to clot properties with specific attention to: 1) transfusions within the first 24 hours of surgery, 2) 24-hour chest tube output, 3) clinical signs and symptoms of postoperative thrombosis. Our multi-site prospective, randomized control trial demonstrated that FC can reduce allogenic blood transfusion in neonates and infants undergoing elective cardiac surgery with CPB when compared to cryoprecipitate. Our proposed laboratory studies use platelet poor plasma to enable us to focus on the contribution of supplemental fibrinogen to neonatal clot kinetics. However, since platelets, particularly the increased dependence on vWF in neonates, also play an important role in post-bypass hemostasis, we plan to correlate clinical characteristics and outcomes with our findings regarding clot kinetics. Clinical outcome variables will be collected for each patient and correlated to clot properties with specific attention to 1) transfusion requirements intraoperatively; 2) transfusion requirements within the first 24 hours of surgery; 3) post-operative bleeding recorded by 24 hour chest tube output; 4) clinical signs and symptoms indicative of postoperative thrombosis; 5) mechanical ventilation time; 6) length of ICU and hospital stay 7) adverse events within seven days of surgery. While our study is not powered to for this outcome, we hope that these data will provide some insight in to the clinical differences between different sources of adult fibrinogen.

Samples Size/Statistical Analysis

Data collected will include demographic data, CBP data, transfusion data, laboratory data and clinical outcomes listed above. As we demonstrated in prior work, neonatal clots prior to transfusion displayed a significantly higher degree of alignment when compared to those composed of adult only or mixed neonatal and adult fibrinogen. Based on our previous data, to detect a difference in degradation times between clots formed with neonatal fibrinogen and clots formed with adult fibrinogen with 80% power, we will enroll a total of 36 patients, with 18 in patients in each arm. All quantitative data will be analyzed using a paired t-test or Wilcoxon rank-sum test to

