### **Analysis of Primary and Secondary Outcomes:**

The primary endpoint of the study is the percentage change of normalized degradation at 24h post-surgery. Primary comparison will be the difference of the primary endpoint between neonates randomized to Cyro and those randomized to FC, with the primary focus on 24h post-surgery time point. To answer this primary research question, we will utilize two sample t-test or Wilcoxon rank sum tests to compare percent change from pre-surgery (baseline) between groups at 24h post-surgery. We will further employ linear mixed models to analyze the longitudinal endpoints accounting for repeated measures. Specifically, we will examine percentage change of normalized degradation at follow up time points (i.e., post-surgery, ICU admission, and 24h post-surgery) relative to baseline between the two groups. Random intercepts at patient level will be included to account for within-subject correlation. Post-hoc comparison between time points will be conducted by contrasts. Results will be presented as difference in least square means between groups or between time points, with associated 95% confidence intervals. Analysis of secondary outcomes, including measurements collected post-transfusion, will be analyzed using similar methods.

Finally, two sample t-tests or Wilcoxon rank sum tests will be used to examine the difference in clot kinetics (i.e., structure, polymerization, degradation) and clinical outcomes including chest tube output, 24-transfusion needs, and ICU length of stay. Two-sample t-tests or Wilcoxon rank sum tests will be used to compare measures between patients with and without thrombotic events. Multivariable linear regression for continuous outcomes and logistic regression for binary outcomes will be used to examine the association between the clot kinetics and clinical outcome while adjusting for potential confounders including pre-surgical weight, age, cardiac diagnosis/ RACHS score, and pre-operative comorbid conditions, as needed.

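### Red-cell rules differ by cyanotic status, but the planned comparison of 24-hour transfusion does not adjust for it, which gives up some precision

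*Protocol*

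**What the plan says.** - **Red-cell rule** (Protocol, Transfusion Algorithm): "RBCs will be transfused for hematocrit <32% for acyanotic neonates, while cyanotic neonates are transfused RBCs for a goal Hct 35-40" (per cent). Its scope is wide: "a transfusion algorithm and transfusion thresholds will be followed in the operating room and ICU for all patients enrolled in the study".
- **Eligibility** (Protocol, Study Population): "Neonates undergoing elective cardiac surgery requiring CPB at Children's Healthcare of Atlanta". No criterion restricts entry to cyanotic or acyanotic lesions.
- **Randomization** (Protocol, Randomization): 1:1, and "patients will be randomized using block randomization with variable blocks". No stratification factor is named.
- **Size** (Protocol, Samples Size/Statistical Analysis): "we will enroll a total of 36 patients, with 18 in patients in each arm".
- **Outcome** (Protocol, Aim 2): the list includes "transfusion requirements within the first 24 hours of surgery", not limited to red cells. The same section says the study is not powered for the clinical outcomes.
- **Test** (SAP, Analysis of Primary and Secondary Outcomes): two-sample t-tests or Wilcoxon rank-sum tests for "clinical outcomes including chest tube output, 24-transfusion needs, and ICU length of stay". The sentence does not name the groups; I read it as the comparison between arms.
- **Nearby covariates**: the same SAP section lists cardiac diagnosis or RACHS score as an as-needed confounder in the regressions of clinical outcome on clot kinetics. The SAP's Exploratory Subgroup Analysis includes underlying morphology. Neither document names cyanotic status as an analysis variable.

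**The concern.** An infant with a hematocrit of 33% or 34% is above the acyanotic trigger but below the cyanotic goal. At the same bleeding and the same clot properties, red-cell use can therefore depend on cyanotic class. The algorithm standardises care within each class but builds a difference between classes into the transfusion outcome, and the planned test leaves that difference in the error term.

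Two things are at stake. In the comparison of arms, precision is lost and an uneven split of cyanotic infants can move the estimate in the one trial that is run. In Aim 2, the same variation blurs the link between clot properties and transfusion. Hypothesis 2 predicts no difference in transfusion requirements by degradation time, so avoidable noise makes the predicted null easier to obtain.

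**Working it through.** **1. The plan's own figure.** SAP, Sample Size Considerations: two-sided 5%, two-sample t-test, 1 SD difference. Noncentral-t power is 0.781 with 16 per group, 0.807 with 17 and 0.830 with 18. So 17 completers per group is right, and one lost per group gives 18 and 36 in all. This is for clot degradation; no figure is stated for transfusion.

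**2. Inputs the documents do not give (assumed).** Cyanotic share *p* = 30-90%. Gap *g* between cyanotic and acyanotic mean red-cell volume = 0.5-1.5 within-class SD. Arm effect = 0.8 within-class SD. The gap cannot be derived from the rule, because one class has a trigger and the other a goal.

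**3. Chance imbalance.** With *K* cyanotic infants among 36, the number in one arm is hypergeometric(36, *K*, 18). The difference between arms has the same parity as *K*.

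| *K* of 36 | Difference | Probability |
|---|---|---|
| 18 | 4 or more | 32% |
| 18 | 6 or more | 9% |
| 11 or 25 | 5 or more | 15% |
| 29 | 5 or more | 9% |

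A difference of 4 is 4/18 = 0.22. It moves the unadjusted arm difference by 0.22 × *g*: 0.11 SD at *g* = 0.5, 0.22 SD at *g* = 1, 0.33 SD at *g* = 1.5. The within-class standard error is √(2/18) = 0.33 SD.

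**4. Unadjusted power for red-cell volume.** The variance is multiplied by V = 1 + *p*(1 − *p*)*g*². The noncentrality is (0.8/√V) × √(18/2) = 2.4/√V, with 34 degrees of freedom. Example: *p* = 0.5 and *g* = 1 give V = 1.25 and noncentrality 2.15.

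| Share | *g* = 0.5 | *g* = 1 | *g* = 1.5 |
|---|---|---|---|
| 30% or 70% | 62.3% | 56.4% | 48.5% |
| 50% | 61.9% | 55.0% | 46.3% |
| 60% | 62.0% | 55.3% | 46.8% |
| 80% | 62.8% | 58.1% | 51.6% |
| 90% | 63.5% | 60.8% | 56.6% |

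**5. Adjusted power.** If the class difference is removed in full, V = 1, the noncentrality is 2.4 and power is 64.5%, about 65%. That is a ceiling. The covariate uses one degree of freedom (33 left), and under randomization the expected squared correlation between arm and class is 1/35. The noncentrality then falls to about 2.4 × √(34/35) = 2.37, and power to about 63%. Adjustment gains nothing useful at *g* = 0.5 and is about neutral at a 90% share. At shares of 30-80% it gains roughly 5 to 8 points at *g* = 1 and 12 to 17 points at *g* = 1.5.

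**6. Validity.** Simulation of 5,000 trials per setting (18 per arm, shares 50% and 70%, gaps 0.5, 1 and 1.5 SD) gave type I error of 0.048-0.050 unadjusted and 0.046-0.051 adjusted. At a 1 SD arm effect and a 50% share, power went from 0.81 to 0.82, 0.74 to 0.82 and 0.65 to 0.82 for the three gaps, the same pattern as in steps 4 and 5.

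**The case against.** The strongest reply has four parts.

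- **There is no bias.** A reader might infer that the omitted factor biases the comparison or invalidates the test. It does neither: type I error stays near 5%, and ordinary chance imbalance is already part of the unadjusted standard error. This stands in full.
- **The SAP already has near proxies.** A reader might infer that it ignores lesion type altogether. It does not: it lists cardiac diagnosis as well as RACHS score, and plans stratified and interaction analyses by morphology. This stands in part. The first is optional, is offered as an alternative to a risk score, and sits only in the clot-kinetics models. The second is exploratory and not defined in terms of cyanosis. Neither puts cyanotic status into the planned comparison of arms.
- **The harm rests on assumptions and on red cells alone.** This stands. The listed outcome covers all transfusions, so the rule acts on only part of it, and the effect on the total cannot be computed from the documents.
- **The outcome is minor.** The protocol says the study is not powered for it, and the SAP treats secondary p-values as descriptive. This limits the weight of the point. It does not remove it, because a descriptive estimate is also better for being more precise, and the protocol hopes these data will show clinical differences between fibrinogen sources.

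Weight, age and comorbidity could be proposed as covariates in the same way. Cyanotic status differs in that the protocol itself makes red-cell use depend on it.

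**Conclusion.** The point holds as a matter of precision in a secondary outcome. A baseline factor that the protocol ties to red-cell transfusion is absent from the planned comparison of 24-hour transfusion, and nothing else in the SAP secures its inclusion. Under the assumed ranges, power for red-cell volume is about 46-64% unadjusted against a ceiling of about 65% adjusted, or about 63% once the cost of the covariate is counted. The gain is material only if the gap is near 1 SD or more and the population is mixed. The documents do not settle either condition.

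The documents do not support a reading that the primary result or the sample size is affected. The primary endpoint is clot degradation at 24 hours, its 17 completers per group reproduce, and this argument does not touch it.

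**What to change.** In the SAP, Analysis of Primary and Secondary Outcomes:

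1. Within the 24-hour transfusion outcome, report red cells separately from haemostatic products (platelets, plasma, fibrinogen source).
2. Compare red-cell transfusion between arms in a linear model with cyanotic status (yes/no) as a fixed covariate, or by a rank-sum test stratified on it (van Elteren).
3. In Aim 2 models whose outcome includes red cells, state that cyanotic status is the form in which cardiac diagnosis enters, in place of the present choice between diagnosis and RACHS score.
4. Define the variable as the class used to apply the red-cell rule, recorded before randomization so that it is a true baseline covariate.

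The cost is SAP wording and one degree of freedom per model. The class has to be known to apply the algorithm, so no new measurement is needed. Separating red cells adds one descriptive summary to an already long list of secondary outcomes. The transfusion rule, randomization, primary analysis and sample size stay as they are.

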After enrollment in our study, patients will be randomized to receive either cryoprecipitate or fibrinogen concentrate as part of our transfusion protocol. Our standard transfusion algorithm for neonates includes a quarter to half a unit of platelets and two units of cryoprecipitate, which historically resulted in a median post-operative fibrinogen level of 345mg/dL (258-469) (unpublished data). Using recent studies as well as our historical data, we chose a post-transfusion target fibrinogen level of 300mg/dL. After separation from bypass, patients will receive platelets and *either* cryoprecipitate or FC. For patients randomized to the FC arm, we will calculate the dose of fibrinogen concentrate to achieve a level of 300mg/dL after drug administration using the following equation from Riastap ® Package insert (5):

$$\text{Dose} = \frac{\text{Target Level} - \text{Measured Level}}{1.7 \times \text{weight(kg)}}$$

In order to account for the hemodilutional effects of the bypass prime on fibrinogen levels, the “measured level” will be the fibrinogen level measured after 10min on CPB. If a patient in either arm continues to have post-bypass bleeding, the anesthesiologist will use point of care testing and the transfusion thresholds outlines in the transfusion algorithm to determine appropriate products for transfusion.

Sample Procurement and Processing– At Children’s Healthcare of Atlanta, whole blood samples will be collected from 36 neonates scheduled for elective cardiac surgery requiring CPB. We will collect these samples at four time points: 1) after induction of anesthesia prior to CPB; 2) after termination of CPB and transfusion of platelets and either cryoprecipitate or fibrinogen concentrate; 3) upon arrival to the ICU 4) 24 hours post-operatively in the ICU. These samples will be centrifuged to yield platelet poor plasma (PPP) and stored at -80°C. These samples will be utilized for the clot analysis experiments described in detail below. Samples will be transported according to appropriate regulations to the laboratory of [name] at North Carolina State University for analysis. All samples will be obtained from an arterial line that is required for the planned surgical procedure.

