Analysis of coagulation factors – For each sample, we will measure coagulation factor levels (thrombin, FXIII, vWF, and fibrinogen) using ELISA to elucidate the contribution of these factors present in cryoprecipitate to clot kinetics when compared to FC. Each sample will be analyzed in triplicate to ensure that reproducible and statistically significant data are obtained.

Analysis of clot characteristics - Clots formed from pre-CPB PPP, post-CPB PPP after transfusion of cryoprecipitate or FC, and 24 hours post-operative PPP will be analyzed to compare the effects of FC and cryoprecipitate on clot properties. Using previously described methods, strength parameters will be assessed by rheology and atomic force microscopy (AFM) and polymerization will be determined by thrombin-initiated turbidity/absorbency curves (13). These studies will allow us to directly compare differences between fiber alignment (3-D branching structure), strength, and polymerization differences after the transfusion of FC or cryoprecipitate in neonates after CPB surgery.

Analysis of fibrin fiber alignment – We will quantify clot fiber alignment using an application of an algorithm based on a fast Fourier transform (FFT) that our group has

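### As printed, the fibrinogen-concentrate dose equation divides by body weight and has no unit; followed literally, it closes less than half of the gap to 300 mg/dL in a 3 kg infant

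*Protocol*

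**What the plan says.** The Protocol's Transfusion Algorithm section sets the goal: "we chose a post-transfusion target fibrinogen level of 300mg/dL". For the FC arm it continues: "we will calculate the dose of fibrinogen concentrate to achieve a level of 300mg/dL after drug administration using the following equation". The equation, attributed to the package insert, appears as

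Dose = (Target Level − Measured Level) / (1.7 × weight (kg)).

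The measured level is the one taken 10 minutes into bypass. No unit is given for the dose or for 1.7. Nowhere else do the Protocol or SAP restate the rule, give a mg/kg dose or work an example.

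The comparator is a fixed regimen of two units of cryoprecipitate with platelets. The same section reports a historical median post-operative level of 345 mg/dL (258 to 469) with it.

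The SAP (Analysis of Primary and Secondary Outcomes) will use "two sample t-test or Wilcoxon rank sum tests to compare percent change from pre-surgery (baseline) between groups at 24h post-surgery".

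**The concern.** A dose meant to reach a given plasma concentration must rise with the volume it fills, and so with weight. The printed form does the reverse if the result is in mg. If it is in mg/kg, total mg does not depend on weight at all.

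This equation defines the experimental treatment. Hypothesis 1B predicts faster degradation at 24 hours with FC, and the Introduction attributes this to the absence of FXIII. The section on clot degradation kinetics reports that mixed neonatal and adult clots degrade more slowly than neonatal-only clots. Giving too little adult fibrinogen in the FC arm alone could therefore push the primary endpoint in the hypothesised direction. A positive result could not then be separated from under-dosing. There is also a care issue: the Protocol itself links low fibrinogen after bypass to more bleeding and transfusion.

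The existing safeguards do not repair this:

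- Rescue products depend on continued bleeding, not on missing 300 mg/dL.
- The Protocol does plan that "we will measure coagulation factor levels (thrombin, FXIII, vWF, and fibrinogen) using ELISA", which would reveal a shortfall but not remove it.
- The primary test is an unadjusted two-group comparison. The confounders named for the later regressions do not include fibrinogen level or dose.

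**Working it through.** **Inputs**

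- Target 300 mg/dL and the printed equation: Protocol, Transfusion Algorithm.
- Blood volume: Protocol, Randomization, describes "up to 50mls of normal saline, 20% of a blood volume in a 3kg neonate". So 50 mL / 0.20 = 250 mL at 3 kg, or 83.3 mL/kg.
- Hematocrit 30%: the bypass section says red cells are added to "achieve and maintain a hematocrit of 30% throughout the duration of CPB".
- Hematocrit 45% as an upper value: "RBC transfusion is not permitted for hematocrit values higher than 45" percent.
- Assumed: measured level 100 mg/dL (the documents give none), all infused fibrinogen stays in the volume, and only the FC increment is counted.

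**Does the printed equation reach its own target of 300 mg/dL?**

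At 3 kg and a measured level of 100, the gap is 200 mg/dL and the printed result is 200 / (1.7 × 3) = 39.2. Total mass is 39.2 mg if the result is mg, or 39.2 × 3 = 117.6 mg if it is mg/kg.

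Rise = total mg / volume in dL. Share of the gap closed = rise / 200.

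| Volume at 3 kg | If mg | If mg/kg |
|---|---|---|
| Plasma, Hct 30%: 1.75 dL | 22.4 mg/dL (11.2%) | 67.2 mg/dL (33.6%) |
| Plasma, Hct 45%: 1.375 dL | 28.5 mg/dL (14.3%) | 85.6 mg/dL (42.8%) |
| Whole blood, as a lower limit: 2.5 dL | 15.7 mg/dL (7.8%) | 47.1 mg/dL (23.5%) |

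The target is not reached under either reading. The gap cancels from the share, so the percentages hold at any measured level. They do not depend on what 1.7 means. Under the mg/kg reading, half the gap would be closed only at a hematocrit of about 53%: 1 − (3/5.1/0.5)/2.5 = 0.529.

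**Where does weight belong?**

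At hematocrit 30%, plasma is 83.3 × 0.70 = 58.3 mL/kg = 0.583 dL/kg. A dose of 1 mg/kg then raises plasma fibrinogen by 1/0.583 = 1.71 mg/dL. This agrees with 1.7 as mg/dL per mg/kg. The gap divided by 1.7 is then already in mg/kg, and weight must multiply.

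**Weight-multiplied form**

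200/1.7 = 117.6 mg/kg, and × 3 kg = 352.9 mg. The rise is 352.9/1.75 = 201.7 mg/dL at hematocrit 30% and 352.9/1.375 = 256.7 at 45%, so the level is 302 to 357 mg/dL. The printed dose is 39.2/352.9 = one ninth of this, or 117.6/352.9 = one third.

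**Other weights (same mL/kg, gap 200)**

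- The printed result is 47.1 at 2.5 kg and 29.4 at 4 kg, so the lighter infant's figure is 1.6 times the heavier infant's. The weight-multiplied totals are 294 mg and 471 mg.
- Share in plasma = 1/(1.7 × weight² × dL/kg) if mg, and 1/(1.7 × weight × dL/kg) if mg/kg, with 0.583 dL/kg at hematocrit 30% and 0.458 at 45%.
- 2.5 kg: 16–21% (mg), 40–51% (mg/kg).
- 4 kg: 6–8% (mg), 25–32% (mg/kg).
- With whole blood as the volume, the lower limits are 11% and 28% at 2.5 kg, and 4% and 18% at 4 kg.
- Under mg/kg at hematocrit 45%, the gap closes fully only at 1/(1.7 × 0.458) = 1.28 kg or below.

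**The case against.** The strongest reply is that the equation may be a typesetting or extraction fault: a page with the fraction over 1.7 and weight set beside it could be read by a program as this form. The controlling source, the package insert, is not available here, and staff may dose from it. The team also reports giving FC to thirty infants in its preliminary study. This stands as a reason to check the original page first, and it makes the clinical effect conditional on someone using the printed form. It does not supply the missing unit.

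The check on 1.7 also depends on the hematocrit chosen. FC is given after bypass, when the thresholds run from 32% to 45%. On the same blood volume, 1 mg/kg then gives 1.76 mg/dL at 32%, 2.0 at 40% and 2.18 at 45%. The agreement at 30% therefore supports the meaning of 1.7 without proving it. The shortfall itself does not rest on that meaning.

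The whole-blood figures are fair to challenge, since fibrinogen is a plasma quantity; the plasma ranges are the better estimate. Hematocrit 45% is a limit on giving red cells, not on the infant's own value. Nor does the less-than-half statement hold at every weight: at 2.5 kg and hematocrit 45%, the mg/kg reading closes 51%.

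Finally, the documents do not define how degradation is normalised, so how far a fibrinogen shortfall would carry into the 24-hour endpoint is unknown. The direction of the risk is clear; its size on that endpoint is not.

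**Conclusion.** The concern holds. The printed equation cannot deliver the level it is said to deliver, and nothing in either document corrects it. For a 3 kg infant the FC increment falls short by a factor of nine (mg) or three (mg/kg). Less than half of the gap is closed on every volume basis tried.

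This rests on the Protocol's implied 250 mL blood volume, full recovery, and a result in mg or mg/kg; nothing in the text supports another unit. The percentages are not predicted final levels, because plasma at re-warming, ultrafiltration and platelets also change the level by an unknown amount. Whether any infant was affected depends on what the bedside dose was calculated from. The rule sets the experimental dose in neonates, so it must be corrected whatever current practice is.

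**What to change.** First confirm the position of weight on the original page and against the cited package insert. Then restate the rule with units:

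- Dose (mg/kg) = (300 − measured level in mg/dL) / 1.7, where 1.7 is mg/dL per mg/kg.
- Total mg = Dose × weight (kg).

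Add one worked example: 3 kg, measured level 100 mg/dL (illustrative), 118 mg/kg, 353 mg in total. Check the order set or pharmacy sheet against it. If any infant was dosed from the printed form, report the dose given and the post-transfusion fibrinogen level by arm, so that readers can judge whether the arms received comparable replacement. The blood-volume statement in the Randomization section needs no change.

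The cost is a one-line amendment with an example and a check of the dosing sheet. No extra patients, samples or procedures are needed.
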